6.3.3 Procedures for collecting patient reported outcomes (PRO)

Appropriate procedures for minimizing bias and enhancing compliance will be followed throughout the study. To ensure this, a study coordinator at each study site will be responsible for the PRO evaluation and a standardized procedure for the administration of the PRO questionnaires will be applied. The patient will complete the questionnaires independently, so that the responses reflect the patient’s perception and views rather than those of family, friends, staff, or others.

Each study site will have a designated quiet space in the clinic for the patients to complete the questionnaires at each visit. The questionnaires should be completed prior to other examinations, before there are substantial professional encounters with transmission of information, such as disease status. Such information may influence the answers that the patients provide on questionnaires. Training will be provided to study personnel to ensure the data quality through the standardized administration of the PRO questionnaires.

The QIDS-SR-16 and S-STS must both be administered prior to the infusion at designated visits.

The PROs of QIDS-SR-16 and SDS are discussed in Sections [6.2.2.1](#) and [6.3.2.2](#), respectively.

6.4 Safety

The PI is responsible for ensuring that all staff involved in the study are familiar with the content of this section.

6.4.1 Definition of adverse events

An AE is the development of an undesirable medical condition or the deterioration of a pre-existing medical condition following or during exposure to a pharmaceutical product, whether or not considered causally related to the product. An undesirable medical condition can be symptoms (eg, nausea, chest pain), signs (eg, tachycardia, enlarged liver), or the abnormal results of an investigation (eg, laboratory findings, ECG). In clinical studies, an AE can include an undesirable medical condition occurring at any time even if no study treatment has been administered.

The term AE is used to include both serious and non-serious AEs.

6.4.2 Definitions of serious adverse events

An SAE is an AE occurring during any study phase (ie, enrollment, treatment, washout, follow-up), that fulfills 1 or more of the following criteria:

- Results in death
- Is immediately life-threatening
- Requires in-patient hospitalization or prolongation of existing hospitalization
- Results in persistent or significant disability or incapacity or substantial disruption of the ability to conduct normal life functions
- Is a congenital abnormality or birth defect
- Is an important medical event that may jeopardize the patient or may require medical intervention to prevent one of the outcomes listed above

For reporting purposes, any suspected transmission via a medicinal product of an infectious agent is also considered an SAE and is reported in an expedited manner. Any organism, virus, or infectious particle (eg, prion protein transmitting Transmissible Spongiform Encephalopathy), pathogenic or non-pathogenic, is considered an infectious agent.

For further guidance on the definition of an SAE, see [Appendix B](#) to the CSP.

Psychiatric hospitalization is at times required and is expected for MDD. If hospitalization is needed due to the exacerbation of, or for the stabilization of, MDD, it will be reported as an SAE. The psychiatric assessments will reflect the worsening of the patient's condition and the need for hospitalization. These hospitalizations will be reported in the eCRF. Further guidance on the reporting of deterioration of the patient's condition with respect to MDD is contained in the following Section 6.4.3. If a patient is hospitalized, the AstraZeneca/ safety review group will decide if the patient is to be discontinued from

the study. Should the patient need to be discontinued from the study, all assessments and procedures required at Week 14 in [Table 4](#) will be conducted.

6.4.3 Recording of adverse events

Time period for collection of adverse events

Adverse events and SAEs will be collected from the time of signature of informed consent throughout the treatment period and follow-up period. In patients who discontinue prior to final visit, unsolicited SAEs will be collected for 30 days post last study treatment.

Follow-up of unresolved adverse events

Any AEs that are unresolved at the patient's last AE assessment in the study are followed up by the investigator for as long as medically indicated, but without further recording in the eCRF. AstraZeneca or its representative retains the right to request additional information for any patient with ongoing AE(s)/SAE(s) at the end of the study, if judged necessary.

Variables

The following variables will be collected for each AE;

- AE (verbatim)
- The date and time when the AE started and stopped
- Maximum intensity or intensity or changes in intensity
- Whether the AE is serious or not
- Investigator causality rating against IP (yes or no)
- Action taken with regard to IP
- AE caused patient's withdrawal from the study (yes or no)
- Outcome

In addition, the following variables will be collected for SAEs:

- Date AE met criteria for SAE
- Date investigator became aware of SAE
- AE is serious due to
- Date of hospitalization
- Date of discharge

- Probable cause of death
- Date of death
- Autopsy performed
- Causality assessment in relation to study procedure(s)
- Causality assessment in relation to IP
- Causality assessment in relation to other medication
- Description of AE

Intensities will be reported for each AE in the following categories:

- Mild (awareness of sign or symptom, but easily tolerated)
- Moderate (discomfort sufficient to cause interference with normal activities)
- Severe (incapacitating, with inability to perform normal activities)

It is important to distinguish between serious and severe AEs. Severity is a measure of intensity whereas seriousness is defined by the criteria in Section 6.4.2. An AE of severe intensity need not necessarily be considered serious. For example, nausea that persists for several hours may be considered severe nausea, but not an SAE. On the other hand, a stroke that results in only a limited degree of disability may be considered a mild stroke, but would be an SAE.

Worsening symptoms of the primary study condition (ie, MDD) should not be recorded as an AE. However, if hospitalization results from worsening psychiatric symptoms, the hospitalization should be recorded as an SAE in the eCRF.

Study drug abuse is an SAE, even when there are no symptoms or additional AEs, and should be reported according to the guidelines in Section 6.4.4. Misuse of IP is an AE, but is not considered an SAE unless accompanied by serious sequelae.

Should an overdose of IP occur, it must be reported in accordance with the procedures described in Section 13.2. An overdose associated with symptoms must be reported as an AE, while an overdose without associated symptoms, must be reported only on the separate AstraZeneca Clinical Study Overdose Report Form.

Suicidality

Any patient who, based on the investigator's judgment, poses an imminent risk of suicide should be discontinued from the study (see Section 5.8 and Section 5.9). All efforts should be taken to minimize the risk of suicide and the investigator should carefully monitor the

patient. If during the course of the study, a patient shows evidence of serious suicidality (for example warranted by a scoring of 4 or 5 on the C-SSRS), the patient should be referred to their attending psychiatrist, a local emergency room etc. for further evaluation to see if they are safe to continue in the study. The site should have the ability to direct any patient that requires emergency hospitalization to an emergency room or inpatient psychiatric unit that is within a 50 mile radius of the site. In addition, the patient should be able to contact someone at the site 24 hours per day should they have serious worsening of their condition.

Suicide and attempted suicide, irrespective of the method, but occurring in connection with the use of IP, should be reported as AEs (serious or nonserious). This event should be identified as suicide or attempted suicide, and the method of the suicide or attempt should be provided. If an attempted suicide meets the criteria for an SAE, the event must be reported according to the guidelines in Section 6.4.4. Strong suicidal thoughts should also be regarded as AEs.

All events of suicidality will be carefully monitored. These include events of suicide attempts, suicidal ideation, completed suicides, and suicidal behavior. The last category includes behavioral AEs or SAEs in which the investigator cannot rule out underlying suicidal thinking, eg, motor vehicle accident or behaving in a dangerous or unsafe way, and other self-injurious behaviors.

Investigators are required to provide detailed accounts of AEs related to, or possibly related to, suicidality as described above, to AstraZeneca or representative promptly according to the guidelines for SAEs in Section 6.4.4 and preferably within 5 days for nonserious AEs. Requested information about these events includes the exact nature of the event and the circumstances of the patient at the time of the event. In addition to the usual information required to document AEs or SAEs, data on all of the above will be collected on separate eCRF pages.

The latest version of the AE dictionary, Medical Dictionary for Regulatory Activities (MedDRA), will be used by the CRO staff for the classification and analysis of AEs entered in the study database. For regulatory reporting, SAEs will be processed in the Global Patient Safety Database Sapphire and coded using MedDRA.

Should a pregnancy occur, it must be reported in accordance with the procedures described in Section 13.3, Pregnancy. Pregnancy in itself is not regarded as an AE unless there is a suspicion that an IP may have interfered with the effectiveness of a contraceptive medication.

Causality collection

The investigator will assess the causal relationship (ie, the relationship to study treatment) between the IP and AEs, and answer “yes” or “no” to the question “Do you consider that there is a reasonable possibility that the event may have been caused by the investigational product?”

Causal relationship in cases where the disease under study has deteriorated due to lack of effect will be classified as no reasonable possibility.

For SAEs, causal relationship will also be assessed. Note that for SAEs that could be associated with any study procedure, the causal relationship is implied as “yes.”

A guide to the interpretation of the causality question is found in [Appendix B](#) to the CSP.

Adverse events based on signs and symptoms

All AEs spontaneously reported by the patient or reported in response to the open question from the study personnel: “Have you had any health problems since the previous visit?” or revealed by observation will be collected and recorded in the eCRF. When collecting AEs, the recording of diagnoses is preferred (when possible) to recording a list of signs and symptoms. However, if a diagnosis is known and there are other signs or symptoms that are not generally part of the diagnosis, the diagnosis and each sign or symptom will be recorded separately.

Adverse events based on examinations and tests

The results from protocol-mandated laboratory tests and vital signs will be summarized in the CSR. Deterioration as compared with baseline in protocol-mandated laboratory values and vital signs should therefore only be reported as AEs if they fulfill any of the SAE criteria or are the reason for discontinuation of treatment with the IP.

If deterioration in a laboratory value/vital sign is associated with clinical signs and symptoms, the sign or symptom will be reported as an AE and the associated laboratory result/vital sign will be considered as additional information. Wherever possible, the reporting investigator uses the clinical, rather than the laboratory term (eg, anemia versus low hemoglobin value). In the absence of clinical signs or symptoms, clinically relevant deteriorations in non-mandated parameters should be reported as AE(s).

Any new or aggravated clinically relevant abnormal medical finding at a physical examination as compared with the baseline assessment will be reported as an AE.

NB. Cases where a patient shows an AST **or** ALT $\geq 3x$ ULN **or** total bilirubin $\geq 2x$ ULN may need to be reported as SAEs, please refer to [Appendix E](#) “Actions Required in Cases of Combined Increase of Aminotransferase and Total Bilirubin – Hy’s Law” for further instructions.

Disease progression or worsening depression

Disease progression can be considered as a worsening of a patient’s condition attributable to the disease for which the IP is being studied. It may be an increase in the severity of the disease under study and/or increases in the symptoms of the disease. The development of worsening depression should be considered as disease progression and not an AE. Events, which are unequivocally due to disease progression, should not be reported as an AE during the study.

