The comparator in this study is placebo (0.9% saline), which will also be administered intravenously. The infusion will be a final volume of 100 mL given at an infusion rate of 1.67 mL/min over 60 minutes. Patients assigned to the placebo treatment group will receive multiple infusions of placebo during the treatment period according to the same schedule as the patients assigned to the AZ6765iv dose groups.

Duration of treatment

Eligible patients will have a screening period of up to 6 weeks. Following the screening period, patients will enter a 12-week double-blind treatment period and a 14-day follow-up period.

Outcome variables:

- **Efficacy**

Primary outcome variable:

- Change from baseline to Week 6 in the MADRS total score

Secondary outcome variables:

- Change from baseline to Week 12 in the MADRS total score
 - Percentage of patients with sustained response, defined as a $\geq 50\%$ reduction from baseline in the MADRS total score at Week 6 and which is maintained through Week 12
 - Change from baseline in the MADRS total score at each scheduled assessment
 - Percentage of responders at each scheduled assessment where responders are defined as patients with a $\geq 50\%$ reduction from baseline in MADRS total score
 - Percentage of patients who are remitted at each scheduled assessment where remission is defined as MADRS total score ≤ 8
 - Change from baseline in functional impairment at each scheduled assessment, as measured by the change from baseline in the SDS total score
 - Change in severity of depressive symptoms at each scheduled assessment as measured by change from baseline in the CGI-S score
 - Change in severity of depressive symptoms at each scheduled assessment as measured by the CGI-I response. Response in CGI-I is based on whether or not the CGI-I score is ≤ 2 (very much improved or much improved).
 - Change from baseline in self-rated severity of depressive symptoms at each scheduled assessment as measured by QIDS-SR-16 total score
- **Safety**
 - Adverse events (AEs)/serious adverse events (SAEs), including their severity
 - AEs leading to treatment discontinuation or study withdrawal

- Suicidality as measured by AEs of suicidality, suicidal ideation, suicide attempts, and suicide completion
- Other significant AEs (OAEs), other AEs of special interest
- Change from baseline in physical examination results, weight, body mass index (BMI), vital signs, clinical laboratory test results, and ECG results

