1.3 Rationale for conducting this study

The overall rationale for this study is to assess the acute and sustained antidepressant effect of adjunctive AZD6765iv in patients with MDD who have a history of inadequate response to currently available antidepressants. Inadequate response is defined as persistent symptoms that, as judged by the investigator, continue to meet the diagnostic criteria for a Major Depressive Episode according to Diagnostic and Statistical Manual of Mental Disorders, 4th edition, Text Revision (DSM-IV-TR).

A previous study (Study D6702C00009) demonstrated an acute antidepressant effect of AZD6765 when administered 3 times per week for 3 weeks. However, the effect was not sustained beyond 2 weeks after the last infusion. Therefore in the current study, following the initial 3 infusions per week for 3 weeks dosing regimen, the dose administration will be tapered to once-weekly infusions during Weeks 4 to 6 and once every other weekly infusions during Weeks 8 to 12 (Week 7 has no infusion scheduled) in an effort to sustain the antidepressant effects of AZD6765.

In an attempt to expand the options currently available for the treatment of MDD and to build upon existing clinical data observed with the use of NMDA antagonists to exert an antidepressant effect, the current study will explore the use of AZD6765 at a dose of 50 mg and 100 mg given in the treatment of MDD.

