3.1.3 Follow-up Visit

As implemented by Amendment 2, patients will be scheduled for a 14 (\pm 4 days)-day follow-up visit (Week 14) from last dosing to collect laboratory measurements and other assessments as detailed in [Table 4](#), including CogState.

Patients who have completed the infusions prior to implementation of Amendment 2, but are still within the 14 (\pm 4 days)-day window from last dosing, will have a 14 (\pm 4 days)-follow-up visit (Week 14), regardless of whether they have completed assessments scheduled for Week 13 (Visit 17) under the previous protocol amendment. Patients who have completed assessments scheduled for Week 13 (Visit 17) under the previous protocol amendment do not need to repeat any laboratory assessments.

Patients who have completed the infusions and are outside the 14 (\pm 4 days)-day window from last dosing at the time of implementation of Amendment 2 will be considered complete. These patients may return to the site for an unscheduled follow-up visit at the discretion of the investigator.

Table 4 Study assessments through the treatment period

	Enroll- ment		Treatment Period															
	Screen/ Washout	R															EOT	Follow- up ^b
Visit	1 ^a	2	3	4	5	6	7	8	9	10	11	12	13	14	15	16		
Infusion		1	2	3	4	5	6	7	8	9	10	11	12	13	14	15		
Week	-6 to -1	Week 1			Week 2			Week 3			W4	W5	W6	W8	W10	W12	W14	
Day (±x days)	-42 to -1	non-consecutive days									(±2)	(±2)	(±2)	(±4)	(±4)	(±4)	(±4)	
Informed consent	X																	
Inclusion/exclusion criteria	X	X																
Demography	X																	
Psychiatric (including number of depressive episodes) and family history	X																	
Prior and concomitant medication	X	X	X	X	X	X	X	X	X	X	X	X	X	X	X	X	X	
Medical and surgical history	X																	
Alcohol and drug history	X																	
ATHF	X																	
Employment status	X	X															X	
Vital signs (supine)	X	X ^c	X ^c	X ^c	X ^c	X ^c	X ^c	X ^c	X ^c	X ^c	X ^c	X ^c	X ^c	X ^c	X ^c	X ^c	X ^c	
Orthostatic BP ^d		X	X	X	X	X	X	X	X	X	X	X	X	X	X	X		
Physical examination		X															X	

Table 4 Study assessments through the treatment period

	Enroll- ment		Treatment Period															
	Screen/ Washout	R															EOT	Follow- up ^b
Visit	1 ^a	2	3	4	5	6	7	8	9	10	11	12	13	14	15	16		
Infusion		1	2	3	4	5	6	7	8	9	10	11	12	13	14	15		
Week	-6 to -1	Week 1			Week 2			Week 3			W4	W5	W6	W8	W10	W12	W14	
Day (±x days)	-42 to -1	non-consecutive days									(±2)	(±2)	(±2)	(±4)	(±4)	(±4)	(±4)	

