If a patient discontinues from the study before completion and has received at least 1 dose of IP, the patient will be asked to return for scheduled study-related visits for the remainder of the study. If they discontinued during Weeks 1 to 3 when there are 3 scheduled visits per week, they will only be asked to return to the site once a week. The following assessments will be obtained at each visit: MADRS, CGI-S, CGI-I, C-SSRS, AEs, and concomitant medications according to the schedule displayed in Table 4 whenever possible. Every effort should be made to follow up with patients who discontinue from the study prior to Week 12. If patients refuse to return to the clinic for the study-related assessments, a modified follow-up through, for example, regular telephone contact or a contact at study closure should be arranged, if agreed to by the patient and in compliance with local data privacy laws/practices. If the patient refuses follow-up, the reason for the refusal and last contact date should be documented in the eCRF and source documents.

The investigator must notify AstraZeneca or representative of any hospitalization. Hospitalization is an SAE and should be reported as described in Sections 6.4.2 and 6.4.4. If a patient is hospitalized, the AstraZeneca safety review group will decide if the patient is to be discontinued from the study. Should the patient need to be discontinued from the study, all assessments and procedures required at Week 14 in Table 4 will be conducted.

Patients who discontinue from the study will not be replaced.

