11.2 Calculation or derivation of safety variables

A treatment-emergent AE (TEAE) is defined as any AE that started on or after the first dose of IP up to 30 days after the last dose of IP. An AE already present at the time of the first dose of IP that worsens in intensity following exposure to IP or an AE with an unknown/not reported onset date will also be considered as treatment emergent.

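### Treatment-emergent AEs are defined to 30 days after the last dose, but collection in completers ends at 10 to 18 days, and the incidence tables follow a third rule

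*Protocol*

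**What the plan says.** Section 11.2 of the protocol defines a treatment-emergent AE as "any AE that started on or after the first dose of IP up to 30 days after the last dose of IP". It adds AEs that were already present and worsened, and AEs with no known onset date.

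The general collection rule is in Section 6.4.3: "Adverse events and SAEs will be collected from the time of signature of informed consent throughout the treatment period and follow-up period". The follow-up period is short. The synopsis (Duration of treatment) says that "patients will enter a 12-week double-blind treatment period and a 14-day follow-up period". Section 3.1.3 schedules a single visit at 14 (±4) days, described as a "follow-up visit (Week 14) from last dosing to collect laboratory measurements" and other assessments. Table 4 shows no contact after it.

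Section 6.4.3 then adds a rule for one group: "In patients who discontinue prior to final visit, unsolicited SAEs will be collected for 30 days post last study treatment". Section 5.9 says of a dosed patient who leaves the study early that "the patient will be asked to return for scheduled study-related visits for the remainder of the study". The assessments at those visits are "MADRS, CGI-S, CGI-I, C-SSRS, AEs, and concomitant medications according to the schedule displayed in Table 4 whenever possible". Section 5.8 keeps patients who stop only the infusions on the normal schedule. Both sections offer a reduced follow-up, for example by telephone, to patients who will not attend.

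Section 12.2.4 tabulates crude incidence. A patient counts once for an event at any time from the day of randomization, over all randomized patients exposed. It states no upper time limit and no person-time denominator.

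**The concern.** The protocol classifies events over a longer period than it collects them in the patients expected to be the majority. After the Week 14 visit a completer has no scheduled contact and no stated rule for SAE collection, although the sponsor treats 30 days as the relevant SAE period for patients who leave early. A serious event on Day 25 after the last dose is therefore captured in a discontinuer but has no stated rule in a completer.

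Two other provisions do not close the gap. Section 6.4.2 ties SAEs to study phases, of which follow-up is the last named. Section 6.4.4 covers SAEs arising in the course of the study, and a completer's last visit has passed.

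What is at stake is how post-treatment safety counts are read, including suicidality, which the synopsis names as a safety outcome. In a crude incidence table, days without observation look the same as days without events. The number of post-dose days observed depends on how the patient left treatment.

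**Working it through.** The plan gives no figure to reproduce here. The check is day arithmetic and a side-by-side reading of the rules.

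**Inputs**
- Treatment-emergent limit: 30 days after the last dose (Section 11.2).
- Last AE collection in completers: 14 ± 4 days, that is 10 to 18 days (Section 3.1.3, Table 4).
- Randomized: 282. Expected dropout: 14% by Week 6 and an additional 10% by Week 12 (Section 12.3).
- Assumed nominal dosing days: Infusions 1-9 on Days 1 to 19, then three intervals of 7 days and three of 14 days. The last dose falls on Day 19 + 21 + 42 = 82, and the Week 14 visit on Day 82 + 14 = 96.

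**Gap in completers**

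Uncollected days = 30 − visit day. The whole window from first dose to last dose + 30 days is (82 − 1) + 30 = 111 days.

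| Visit, days after last dose | Uncollected days | Share of 30-day tail | Share of whole window |
|---|---|---|---|
| 10 | 20 | 20/30 = 67% | 20/111 = 18% |
| 14 | 16 | 16/30 = 53% | 16/111 = 14% |
| 18 | 12 | 12/30 = 40% | 12/111 = 11% |

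**Number affected**

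282 × (1 − 0.24) = 214 completers. If the second 10% is taken of those remaining, 282 × 0.86 × 0.90 = 218.

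**Discontinuers who keep attending to Week 14**

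All AEs are collected for 96 minus the last dose day:
- last dose Day 19: 96 − 19 = 77 days
- last dose Day 40: 96 − 40 = 56 days
- last dose Day 68: 96 − 68 = 28 days

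Most or all of the 30-day tail is covered for them, and often more.

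**Rules side by side**

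| Patient | Collected after the last dose |
|---|---|
| Completer | All AEs and SAEs to 10-18 days, then no rule |
| Discontinuer who returns | All AEs at remaining visits, possibly beyond 30 days |
| Discontinuer who refuses all contact | Unsolicited SAEs to 30 days; no rule for non-serious AEs |

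**Definition against table**

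An AE on Day 40 after the last dose in a returning discontinuer is collected. It is not treatment-emergent under Section 11.2, yet it enters the numerator in Section 12.2.4. The starting points differ too: first dose in Section 11.2, day of randomization in Section 12.2.4.

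**The case against.** The best defence is that a treatment-emergent limit classifies events and does not create a duty to collect them. If the limit is longer than collection, every post-dose AE collected in a completer is still classed as treatment-emergent, and none is misclassified. This is correct. What it leaves is that completers have no SAE rule for days that the definition includes, while discontinuers do.

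A reader might infer several stronger things that the documents do not support.

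- *That half the safety window is empty.* The 40-67% applies only to the tail after the last dose in completers. Over the whole window the gap is about 11-18%.
- *That discontinuers have nothing but unsolicited SAEs collected.* Section 6.4.3 does not restrict collection in that way. Its sentence can operate beside Sections 5.8 and 5.9, as a backstop for patients who do not return. It need not be deleted.
- *That the arm with more discontinuations is bound to look worse.* The completer rule is the same in every arm, so bias needs discontinuation or return to differ by arm. Nor is total observation always longer in a discontinuer: one who stops on Day 19 and does not return has SAE cover to about Day 49, against about Day 96 for a completer.
- *That collection stops just as relapse would appear.* Section 1.3 does say of the previous study that "the effect was not sustained beyond 2 weeks after the last infusion", but that followed infusions three times a week for 3 weeks. Here infusions are already two weeks apart from Week 6 on, with AEs and the C-SSRS recorded at each visit. Worsening depression is not recorded as an AE unless it leads to hospitalization (Section 6.4.3).

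A 14-day follow-up can also be defended on the half-life of 11 to 14 hours in Section 1.1.2.2. The point is therefore the disagreement between sections, and not that 14 days is too short.

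**Conclusion.** The point stands as an inconsistency in the protocol of moderate importance. Sections 6.4.3, 11.2 and 12.2.4 use three different post-dose periods. In about 214 expected completers, 12 to 20 of the 30 post-dose days have no collection rule, SAEs included. The mismatch concerns what data are gathered, so an analysis plan written later cannot supply the missing events.

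It does not touch the primary endpoint, and the documents give no evidence of bias between arms.

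The size rests on the expected 24% dropout, on completers attending the Week 14 visit within its window, and on the assumed last dose near Day 82. The 10-18 days is the Amendment 2 schedule. Patients already outside that window when the amendment took effect are considered complete under Section 3.1.3, and how long they were followed is not given.

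**What to change.** Reconcile Sections 6.4.3, 11.2 and 12.2.4 in one of two ways.

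1. **Extend collection.** Apply the existing 30-day SAE rule in Section 6.4.3 to every dosed patient, completers included. This needs a brief contact about two weeks after the Week 14 visit, for example by telephone, for about 214 patients, and moves last contact later by the same amount. Section 11.2 should then say that the 30 days applies to SAEs and where the window for non-serious AEs ends.
2. **Shorten the definition.** Set the treatment-emergent window in Section 11.2 to the post-dose period actually collected. This costs only wording, but leaves later SAEs in completers without a rule.

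With either choice, apply one post-dose cut-off to completers and discontinuers in the Section 12.2.4 incidence tables, start the count at the first dose as in Section 11.2, and list later events separately. The discontinuer rule in Section 6.4.3 can stay, and no additional C-SSRS rating is needed.
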